## **Study design and description**

This work is designed as a randomized, sham-controlled clinical trial in which we monitor the effects of low-energetic focused shock wave therapy (ESWT) on Achilles (AT) tendinopathy. We estimate that at least 18 patients will participate in it. They will be randomly divided into two groups in 1:1 ratio. Group A will receive ESWT according to selected parameters (see below). Group B will receive placebo in the means of sham-ESWT (see below).

Patients in both groups will have same program. The research within one patient will last in total of 8 weeks from the initial to the end examination. In the initial week the patient will be clinically examined by a physiotherapist, an ultrasonography (USG) examination will be performed and VISA-A questionnaire will be filled. At the end of this session, the patient will be randomly assigned to group A or B and receive first application (ESWT or sham-ESWT). For the next 4 weeks, once a week, the next applications will be performed. The interval between individual applications should be at least 5 days. Thus, a total of 5 applications of ESWT or sham-ESWT will be performed. The final examination will be performed at 3 weeks follow up after the last application and includes the same procedures as in the initial examination.

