## **Initial and final examination**

During the initial and final examinations, the several tasks to the patient will be performed. Firstly the anamnestic data will be collected, then the ankle dorsiflexion range of motion will be measured using the "weight-bearing lunge test" (cm). Thompson's test and resistance test will be

performed at the same time. The area of greatest pain will be localized by palpation. Then patient will also perform AT loading tests on both legs — single leg heel rise test and single leg hop test. The patient will perform as many heel rises/hops using only one leg as possible in 30 seconds or until first sign of pain in Achilles tendon area. This will be also measured in asymptomatic leg.

Secondly, the patient will be asked to complete a validated Victorian Institute of Sports Assessment - Achilles questionnaire, which assesses the subjectively perceived severity of the disease and partly its impact on the quality of normal daily or sports activities.

The patient's maximal pain will be assessed using a standardized numerical rating scale (NRS) of pain. The patient will be asked about the maximum pain that could be caused by various factors, at the initial examination, at the last application and during the final examination.

Lastly, the ultrasonographic examination of patient's AT in both legs will be performed. This examination is described in the following chapter.

Both, initial and final examinations in each patient will be performed by only one person (the investigator of the study) and the same person will prepare and perform each application of ESWT or sham-ESWT.

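### VISA-A, and by paragraph order the NRS, are collected after palpation and pain-limited loading tests; completing them first would remove avoidable noise and, at the final visit, narrow a route for cueing

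*Combined protocol and SAP*

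**What the plan says.** Two sections describe what happens at an examination visit.

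- **Study design and description** gives an overview of the initial week: a clinical examination by a physiotherapist, and then "an ultrasonography (USG) examination will be performed and VISA-A questionnaire will be filled". Assignment and the first application come at the end of that session. The final examination repeats the same procedures three weeks after the last application.
- **Initial and final examination** gives a sequence in ordinal words. The first block opens with "Firstly the anamnestic data will be collected" and goes on to the lunge test, Thompson's and resistance tests, and palpation for the most painful area. It ends with loading: "Then patient will also perform AT loading tests on both legs". The stopping rule for loading is that "The patient will perform as many heel rises/hops using only one leg as possible in 30 seconds or until first sign of pain". The second block is the questionnaire: "Secondly, the patient will be asked to complete a validated Victorian Institute of Sports Assessment - Achilles questionnaire". The NRS for maximal pain follows in its own paragraph, without an ordinal word. Ultrasonography is placed last.

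The same section has one person, the investigator, carry out both examinations of each patient and prepare and deliver every application. Patients distribution and randomization keeps patients unaware of their group and places assignment after the initial examination.

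**The concern.** VISA-A and the NRS are the trial's self-reported outcomes, and under Data analysis the results are judged as final against baseline in the two groups. The plan collects VISA-A after tests that may be stopped only when they hurt. A patient who has just been pressed on the sore point and has hopped to first pain may rate the tendon differently from one who fills in the form on arrival.

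Two mechanisms should be kept apart:

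1. **Provocation.** The tests are the same in both arms and at both visits. Their main effect is extra variability or a shift common to both groups, which costs precision more than it creates a group difference. It could differ by group only indirectly, if treatment changes how much pain the tests provoke and that pain then carries into the ratings.
2. **Cueing.** At the final visit the person running the tests has treated the patient and knows the group. Manner or remarks during testing could influence the self-rating that follows. This route can differ by group.

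At stake is some avoidable imprecision in a very small trial, together with one route to bias in the outcomes most open to suggestion.

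**Working it through.** **Step 1: order of procedures, side by side.**

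| | Study design and description | Initial and final examination |
|---|---|---|
| First | clinical examination | history, clinical tests, palpation, loading tests |
| Next | ultrasonography | VISA-A, then NRS (paragraph order only) |
| Last | VISA-A | ultrasonography |
| Sequence words | none | yes, except for the NRS |

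Both listings put VISA-A after the clinical examination. They differ only in where the scan falls. The right-hand column carries the point, because only that section describes the loading tests and their pain limit, "or until first sign of pain in Achilles tendon area".

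**Step 2: when the examiner can know the group.**

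- Initial examination: assignment has not yet happened, so baseline VISA-A and NRS cannot be cued by knowledge of group.
- Last application: the NRS is also asked here. The investigator knows the group, but no loading tests are described.
- Final examination: the investigator knows the group and has just tested the patient.

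Provocation therefore applies at both examinations. Testing by someone who knows the group, followed by the ratings, applies only at the final one.

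**Step 3: illustration of size.** The documents give no SD, significance level, or estimate of noise or cueing, so there is no stated figure to reproduce. Inputs from the documents: "We estimate that at least 18 patients will participate in it" and "They will be randomly divided into two groups in 1:1 ratio", hence 18 / 2 = 9 per arm. Everything else in this step is assumed: two-sided 5% level, a two-sample t-test, and the noise and cue sizes.

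*Noise.* If a share s of the observed variance comes from provocation, the standard error is larger by a factor of 1/√(1 − s):

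- s = 0.10: 1/√0.90 = 1.05, so intervals are about 5% wider.
- s = 0.20: 1/√0.80 = 1.12, so intervals are about 12% wider.

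*Cueing.* With no true effect and a group-related shift of d SD, the t statistic has 2 × 9 − 2 = 16 degrees of freedom, noncentrality d√(9/2) and critical value 2.120.

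| Assumed shift d | Noncentrality | Rejection rate (noncentral t) | Normal approximation |
|---|---|---|---|
| 0 | 0 | 5.0% | 5.0% |
| 0.2 | 0.42 | 6.8% | 7.1% |
| 0.3 | 0.64 | 9.2% | 9.8% |
| 0.5 | 1.06 | 17.0% | 18.6% |

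The t-based column suits 9 per arm. These rates follow mechanically from the assumed shifts and are not evidence that such shifts will occur in this trial.

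**The case against.** The strongest reply is that this is a good-practice preference. The loading tests are identical in both arms, so they do not by themselves favour either group. The NRS asks about maximum pain from various causes, and VISA-A about perceived severity and effect on daily or sports activity. Neither is described as a rating of pain at that moment, so a carry-over from the tests is plausible but not shown. Patients are blinded and kept from seeing the device. Nothing in the plan says the investigator comments on findings to the patient. The investigator will also have met the patient at five applications before the final visit, so reordering one visit cannot undo any impression already given.

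All of this stands as a limit on size. It does not justify keeping the present order, which has no stated reason and could be changed at almost no cost.

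Three stronger readings are tempting, and the documents do not support them:

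- **The examiner is unblinded at both visits.** Assignment follows the initial examination, so there is no group to know at baseline.
- **The two sections conflict, so the order may vary between visits and confound the change scores.** The overview is a short list without sequence words, the difference concerns only the scan, and the final visit is said to repeat the same procedures. Aligning the wording is tidy, but nothing says the order will vary.
- **Every NRS rating follows provoked pain.** Its place after the loading tests rests on paragraph order alone, and no loading tests are described at the last application.

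**Conclusion.** The point holds as a minor one. By the plan's own sequence, VISA-A follows palpation and pain-limited loading at both examinations, and the NRS does so if paragraph order is followed. The likely result is noise or a shared shift. At the final visit only, there is also a limited route for group-related cueing, which patient blinding reduces but does not close.

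Neither effect can be sized from the documents. The illustrative range, 5% to 12% wider intervals and a false-positive rate of roughly 7% to 17%, rests wholly on the assumed noise shares and cue sizes and on 9 patients per arm. No planned analysis becomes invalid. The larger source of possible bias is that one person both treats and assesses, which the order of the forms does not settle.

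**What to change.** In Initial and final examination, state one order for both visits: the patient completes VISA-A and the NRS first, alone and without the investigator's input, before palpation, loading tests, ultrasonography or any discussion of findings. The clinical tests and the scan follow. Align the list in Study design and description with that order.

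This removes the provocation effect from the ratings at both visits. It reduces, but does not eliminate, the bias that can arise when the treating investigator also assesses outcomes; removing that would need a final-visit assessor who does not know the group. The cost of the reordering is a revised visit sheet, with no extra patients, visits or equipment.

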## **Patient selection**

Patients will be included in the study if they meet these inclusion criteria:

- the patient complains about Achilles tendon pain, which limits (at least partially) his quality of life during daily activities or sport, and this condition could be referred as a tendinopathy
- the patient's other leg is asymptomatic
- the patient is not aware of the symptomatic mechanical tendon damage in past (eg. partial or complete rupture due to injury)
- the patient has no previous experience with ESWT

Patients will not be included if:

- the patient has condition which is contraindication for ESWT
- the patient has symptomatic mechanical tendon damage in past (eg. partial or complete rupture due to injury)
- the patient has previous experience with ESWT

## **Patients distribution and randomization**

Patients will be randomly divided into two groups (Group A, Group B) in a 1:1 ratio. Patients in Group A will receive low-energetic focused ESWT according to selected parameters. Patients in Group B will receive placebo (sham-ESWT). The patients themselves will not know which group they are in. Before, during, and even after the session, patients will not be allowed to see the applicator or machine. The sham applicator will have to be always prepared before the patient come into the intervention room.

Due to the fact that AT tendinopathy includes a wider range of causes that can be monitored by USG examination, the finding on USG examination will also be taken into account when dividing into groups. In each group the specific cause should be represented in similar proportion. For this reason, the patient will be assigned to one of the groups only after the initial examination.

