### **Ultrasonographic examination**

USG examination will be performed with a Mindray DC-70 machine with a linear probe type L12-3E with a frequency of 12 Hz in the preset "MSK" mode. The whole area of AT will be monitored from the connection of soleus fibers to the insertion site on the calcaneus by longitudinal and transverse imaging.

The echotexture and continuity of the tendon, the echotexture of KFP, the presence of RC bursa, calcifications and osteophytes will be evaluated visually. At the same time, the possible degree of vascularization in or around the tendon will be evaluated using Doppler mode.

The values of anteroposterior tendon width, paratenon thickness, and CSA at the anteroposterior widest point will be collected using the measuring instruments included in USG machine.

USG findings will be consulted and evaluated in cooperation with an expert in USG diagnostics to increase their relevance and reduce the error rate.

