**Graphically represented study design:**

## **Data analysis**

In this study, the comparison of the results in groups A and B in the final examination compared with the baseline values will be evaluated.

Firstly, descriptive statistics (mean, median, standard deviation, minimum and maximum) of the initial and final values in both groups will be performed. Normal data distribution will be determined by the calculated Shapiro-Wilk p-value.

Then, a two-way ANOVA tests will be used to evaluate the statistical significance of effects comparison in both groups for most of the measured parameters (not including the tendon loading tests). Also the Tukey method will be performed to determine effects of each part of ANOVA testing.

In addition, paired t-tests or the Wilcoxon test will be performed for each group of each parameter. Thus, the statistical significance of the changes in the most of the parameters for each group will be calculated.

The number of repetitions in Achilles tendon loading tests (single leg heel rise / hop test) will only be analyzed by descriptive statistics to see the indicative change in results. There will also be collected a number of those patients who describe the pain during these tests.

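### Allocation takes the USG cause into account, but the planned ANOVA adjusts for neither cause nor baseline; if cause predicts the change in outcome, the test is conservative and power is lost

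*Combined protocol and SAP*

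**What the plan says.** The section on study design and description gives the size and ratio: "We estimate that at least 18 patients will participate in it", and "They will be randomly divided into two groups in 1:1 ratio". The section on patient distribution and randomization adds that "the finding on USG examination will also be taken into account when dividing into groups", with the stated aim "In each group the specific cause should be represented in similar proportion". Assignment is held back until after the initial examination for this purpose. No allocation method is given (strata, blocks or minimisation), and the cause categories are not listed. The ultrasonographic examination section names several features that might define them: "The echotexture and continuity of the tendon, the echotexture of KFP, the presence of RC bursa, calcifications and osteophytes will be evaluated visually".

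The Data analysis section states the target: "the comparison of the results in groups A and B in the final examination compared with the baseline values will be evaluated". The between-group method is that "a two-way ANOVA tests will be used to evaluate the statistical significance of effects comparison in both groups for most of the measured parameters", followed by Tukey comparisons and by paired t or Wilcoxon tests within each group. The two ANOVA factors are not named; the stated comparison suggests group and time. Cause, USG finding, stratum and covariate do not appear anywhere in that section.

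**The concern.** A factor used to balance the arms should normally also enter the analysis. Balancing takes between-cause variation out of the difference between group means. A model without the factor still counts that variation as residual error. The reported standard error then exceeds the true one, intervals are too wide, the type I error falls below nominal and power is lost. With about 18 patients there is little power to spare. The same section also leaves the baseline value out as a covariate, although it is measured on every patient.

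**Working it through.** **Inputs.** From the documents: at least 18 patients, 1:1, so 9 per arm. Not in the documents and therefore assumed: two-sided alpha 0.05, true effect 1.2 SD, no dropout, three causes split 4:3:2 identically in both arms, and R², the share of variance explained by cause, from 0 to 0.3. The plan gives no power calculation behind the 18, so there is no figure of its own to reproduce.

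**Case 1: cause predicts the change.** Set the SD of the change to 1.

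- True SE of the group difference under exact balance: √[(2/9)(1 − R²)].
- Expected residual variance when cause is omitted (16 df): [16(1 − R²) + 18R²]/16 = 1 + R²/8. The reported SE is therefore about √[(2/9)(1 + R²/8)].
- At R² = 0.2: true √(0.2222 × 0.8) = 0.422; reported √(0.2222 × 1.025) = 0.477; ratio 1.13.
- Power with the cause term: noncentral t on 18 − 4 = 14 df, noncentrality 1.2/true SE. At R² = 0.2 this is 1.2/0.422 = 2.85, giving about 75%; simulation gives 75 to 76%.
- Type I error and power without the term are from simulation.

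| R² | True SE | Reported SE, cause omitted | Ratio | Type I error, omitted | Power, omitted | Power, included |
|---|---|---|---|---|---|---|
| 0 | 0.471 | 0.471 | 1.00 | 5% | 66–67% | 65–66% |
| 0.1 | 0.447 | 0.474 | 1.06 | about 4.0% | 67% | 70% |
| 0.2 | 0.422 | 0.477 | 1.13 | about 2.7% | 67% | 75–76% |
| 0.3 | 0.394 | 0.480 | 1.22 | about 2.0% | 68% | 81% |

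**Case 2: cause shifts baseline and final values equally.** The change score removes the shift, whatever its size. Simulated power, with within-cause pre/post correlation 0.5 and an effect of 1.2 times the total outcome SD:

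| R² (of outcome level) | Change score: without / with cause | Baseline as covariate: without / with cause |
|---|---|---|
| 0 | 66 / 65% | 75 / 74% |
| 0.1 | 71 / 71% | 79 / 79% |
| 0.2 | 77 / 76% | 83 / 83% |
| 0.3 | 81 / 80% | 86 / 87% |

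Power rises down the table only because the total SD is held fixed, so the within-cause SD shrinks as R² grows. The cause term adds between about −1 and +1 point. Type I error without it stays at about 4 to 6%.

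The move from change score to baseline covariate adds more. With outcome SD σ and correlation ρ, the variance of a change is 2σ²(1 − ρ), and the residual variance after regression on baseline is σ²(1 − ρ²). At ρ = 0.5 these are σ² and 0.75σ², so the SE falls by a factor of √0.75 = 0.87. That is the step from 66% to 75% in the first row.

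**Case 3: the ANOVA treats the two visits as independent.** The text does not rule this out. With an effect of 1.325 SD of the change, correlation 0.5 and cause explaining 30% of the level, simulated power is 46% without the cause term and 66% with it, against 75% for an analysis that respects the pairing. The lost pairing costs 75 − 46 = 29 points, which is more than the cause term recovers (66 − 46 = 20).

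**The case against.** The strongest objection is that the natural reading of the plan is a group-by-time comparison of change, and there a level difference between causes cancels. The Case 1 losses need cause to predict the change itself, and nothing in the documents shows that it does. This stands, and it sets the limit of the point.

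Second, the plan states an aim, not a working stratification scheme. Identical 4:3:2 splits among 18 patients assigned one at a time are a best case, and several USG features can occur in the same patient. This also stands. It does not remove the case for the term, because adjustment also corrects whatever imbalance remains.

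Third, 18 patients cannot support many terms. That is why the number of categories must stay at two or three. With that limit the cause term costs about 1 point of power at worst.

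Two stronger readings are tempting. A reader might infer that the intervals are certainly too wide and that power is certainly lost. The documents do not support this: they give no prognostic strength for cause, and at R² = 0 the loss vanishes and adjusting costs slightly. A reader might also infer that the omission biases the estimate or raises the false-positive rate. When cause is balanced, the error goes the other way and the test is conservative.

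**Conclusion.** The mismatch is in the text: cause enters the allocation, and neither cause nor a baseline covariate enters the between-group model. Its consequence is conditional. If cause explains 10 to 30% of the variance of the change, about 3 to 13 points of power are forgone (70 − 67 to 81 − 68), and the nominal 5% test runs at about 4% down to 2%. If cause acts equally on both visits or not at all, the cause term is worth about nothing and baseline adjustment carries most of the benefit, about 9 points at an assumed correlation of 0.5. All these sizes rest on assumed effect, alpha, balance, correlation and R², and on ANOVA factors that are inferred. This is a cheap improvement in efficiency and does not threaten validity.

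**What to change.** In Data analysis, replace the between-group ANOVA with a linear model, for each parameter that is to be tested between groups:

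- Outcome: the final value.
- Terms: group, the parameter's own baseline value, and the USG cause category used for balancing.
- Report: the adjusted group difference with its 95% CI.

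In the section on patient distribution and randomization, define two or three mutually exclusive cause categories before the first assignment, and use the same categories in the model.

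Cost: 1 degree of freedom for baseline and 1 or 2 for cause, so 2 to 3 in total. With three categories, 18 − 5 = 13 residual degrees of freedom remain. The cause term costs about 1 point of power at worst. No visit or measurement is added, because the baseline values and USG features are already collected. The real work is writing the category definitions in advance, since the plan has none.

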## **Initial and final examination**

During the initial and final examinations, the several tasks to the patient will be performed. Firstly the anamnestic data will be collected, then the ankle dorsiflexion range of motion will be measured using the "weight-bearing lunge test" (cm). Thompson's test and resistance test will be

performed at the same time. The area of greatest pain will be localized by palpation. Then patient will also perform AT loading tests on both legs — single leg heel rise test and single leg hop test. The patient will perform as many heel rises/hops using only one leg as possible in 30 seconds or until first sign of pain in Achilles tendon area. This will be also measured in asymptomatic leg.

Secondly, the patient will be asked to complete a validated Victorian Institute of Sports Assessment - Achilles questionnaire, which assesses the subjectively perceived severity of the disease and partly its impact on the quality of normal daily or sports activities.

The patient's maximal pain will be assessed using a standardized numerical rating scale (NRS) of pain. The patient will be asked about the maximum pain that could be caused by various factors, at the initial examination, at the last application and during the final examination.

Lastly, the ultrasonographic examination of patient's AT in both legs will be performed. This examination is described in the following chapter.

Both, initial and final examinations in each patient will be performed by only one person (the investigator of the study) and the same person will prepare and perform each application of ESWT or sham-ESWT.

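### The NRS pain rating at the last application has no stated analysis; a baseline-adjusted repeated-measures model would give it a defined, secondary role

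*Combined protocol and SAP*

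**What the plan says.** In the combined protocol and SAP, the section Initial and final examination has maximal NRS pain asked "at the initial examination, at the last application and during the final examination". No other outcome is given a third time point there. According to Study design and description there are five applications, and "The final examination will be performed at 3 weeks follow up after the last application". The two post-baseline ratings are thus about 3 weeks apart.

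The Data analysis section opens by stating that "the comparison of the results in groups A and B in the final examination compared with the baseline values will be evaluated". Descriptive statistics "of the initial and final values in both groups will be performed". For testing, "a two-way ANOVA tests will be used to evaluate the statistical significance of effects comparison in both groups for most of the measured parameters", with no factors or time levels named. A post hoc step follows: "Also the Tukey method will be performed to determine effects of each part of ANOVA testing". Within groups, "paired t-tests or the Wilcoxon test will be performed for each group of each parameter", without naming the pair of visits that applies to NRS.

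On size, Study design and description says "We estimate that at least 18 patients will participate in it", allocated 1:1.

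**The concern.** A rule of baseline against final fits the outcomes measured twice, but it leaves one of the two post-baseline NRS ratings without a purpose. Two things are at stake.

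The first is information. The middle rating is the only scheduled NRS evidence on whether a pain difference is already present around the last application or appears only at follow-up. It is also the only post-baseline NRS value for a patient who does not return for the final examination. In a trial of about 18 patients, both uses deserve a stated place.

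The second is pre-specification. With no ANOVA levels and no visit pair named, three NRS comparisons stay open once data are seen: last application against baseline, final against baseline, and final against last application. The same investigator examines the patients and delivers the real or sham applications, so it is better to fix the choice in advance.

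**Working it through.** **Collection set against analysis.** NRS is collected at 3 time points. The opening sentence of Data analysis and its descriptive statistics name 2 of them. No sentence in that section mentions the remaining one, so 1 of the 2 post-baseline ratings has no stated analysis.

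**No figure of the plan can be reproduced here.** The sample size of at least 18 comes without effect size, SD, alpha or power, and the point does not depend on it.

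**Assumptions for sizing the gain.** 18 patients, 9 per group (from the plan). Equal SD at all three ratings, set to 1, and the same correlation rho between any two ratings, taken as 0.4 to 0.7; the documents give neither.

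**Per-patient variance of the quantity compared between groups:**
- Change from baseline to final: 2(1 − rho). With two time levels and time treated as within-patient, this is what a group-by-time ANOVA interaction tests, so it is the nearest reading of the plan.
- ANCOVA on the final rating: 1 − rho².
- ANCOVA on the mean of both post-baseline ratings: (1 + rho)/2 − rho².
- Change from baseline to that mean: (1 + rho)/2 + 1 − 2·rho = 1.5(1 − rho).

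| rho | change, final | ANCOVA, final | ANCOVA, mean of two | change, mean of two |
|---|---|---|---|---|
| 0.4 | 1.20 | 0.84 | 0.54 | 0.90 |
| 0.5 | 1.00 | 0.75 | 0.50 | 0.75 |
| 0.6 | 0.80 | 0.64 | 0.44 | 0.60 |
| 0.7 | 0.60 | 0.51 | 0.36 | 0.45 |

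**Gain from the baseline covariate, final-visit contrast.** The ratio (1 − rho²)/[2(1 − rho)] equals (1 + rho)/2, so the reduction is (1 − rho)/2: 30%, 25%, 20% and 15% for rho of 0.4, 0.5, 0.6 and 0.7. The covariate costs one residual degree of freedom (18 − 2 = 16 becomes 18 − 3 = 15).

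**Gain from the middle rating, final-visit contrast.** With complete data it is nil: each patient's own final rating is observed, and the earlier one adds nothing beyond a negligible effect through a shared baseline slope. If m of 18 final ratings are missing, spread evenly and at random, and the middle ratings are present, the variance relative to complete cases is 1 − R²·m/18. Here R² is the squared partial correlation of the final and last-application ratings given baseline:

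R² = [(rho − rho²)/(1 − rho²)]² = [rho/(1 + rho)]²

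| rho | R² | gain, m = 2 | gain, m = 4 |
|---|---|---|---|
| 0.4 | 8.2% | 0.9% | 1.8% |
| 0.5 | 11.1% | 1.2% | 2.5% |
| 0.6 | 14.1% | 1.6% | 3.1% |
| 0.7 | 17.0% | 1.9% | 3.8% |

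These are large-sample values; estimating the covariance from 18 patients would erode part of so small a gain.

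**Gain from the middle rating, two-visit average.** Against final-only ANCOVA: 0.30/0.84 = 36%, 0.25/0.75 = 33%, 0.20/0.64 = 31%, 0.15/0.51 = 29%. On change scores: 1 − 1.5/2 = 25% at any rho. Both describe the average effect over two visits, which is not the effect at the final visit.

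**The case against.** The strongest reply is that the plan never says the rating will be dropped. The ANOVA levels are unnamed, so a three-level time factor for NRS is possible, and a reader who infers that the value is discarded goes beyond the text. That stands. The supportable statement is that no analysis is given. The three-level reading is not the natural one, since the opening sentence and the descriptive statistics both point to two time points. It would also still leave the main NRS contrast and the within-patient structure unstated.

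Three other inferences are tempting and fail:
- *The middle rating would make the main result much more precise.* It would not. The 29-36% belongs to the two-visit average, and its comparator is an ANCOVA that the plan does not contain.
- *It is a post-treatment rating.* The text places it at the last application without saying whether the question comes before or after the fifth session. If before, it reflects four applications.
- *A patient who misses the final examination contributes nothing.* The plan states no missing-data rule and no expected dropout.

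It is also fair to say that baseline against final is a legitimate main contrast, and that one sentence declaring the middle rating descriptive would close the gap. A plan that names no primary outcome and no multiplicity control does pay something for extra contrasts. The mixed model is still preferable, because it brings the baseline covariate and a defined place for partial follow-up, provided the additional contrasts are labelled secondary.

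**Conclusion.** The point holds as a low-priority improvement. The last-application NRS has no stated analysis, and a concrete better method than the two-way ANOVA plus within-group paired tests is available on ratings already scheduled.

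For the main contrast, nearly all of the gain comes from baseline adjustment (15-30% lower variance than a change-score comparison). The middle rating contributes nothing with complete data, and about 1-4% if 2 to 4 final ratings are missing. Its real value lies in the time course and in the secondary two-visit average. All percentages rest on equal SDs and an equal correlation of 0.4 to 0.7. The gain with missing ratings further assumes that they are missing at random and evenly spread. No figure in the plan is contradicted.

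**What to change.** In Data analysis:
- Replace the two-way ANOVA for NRS with one repeated-measures mixed model. The outcomes are the last-application and final ratings; the terms are group, visit, group-by-visit and baseline NRS.
- Specify the within-patient covariance (unstructured needs only three parameters for two visits) and a small-sample degrees-of-freedom correction.
- Name the final-visit group contrast as the main NRS result. Label the last-application contrast and the average of the two visits as secondary.
- Add the last-application rating to the descriptive statistics.

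In Initial and final examination, state whether that rating is taken before or after the fifth application.

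The cost is a few sentences and slightly more analysis work. No visit, procedure or patient burden is added. The downside is one or two more secondary contrasts in a small trial.
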